### 6.3.3. Modified Baseline Observation Carried Forward

An mBOCF imputation will be performed on continuous efficacy and health outcome variables. For patients discontinuing study drug due to an AE, the baseline observation at Week 0 in originating study will be carried forward to the corresponding time point for evaluation. For patients discontinuing study drug for any other reason, the last nonmissing observation before discontinuation will be carried forward to the corresponding time point for evaluation. For patients who discontinue originally assigned blinded study treatment and were retreated due to flare, or patients who are escalated from ixekizumab 80 mg Q4W to ixekizumab 80 mg Q2W, the last nonmissing observation prior to the retreatment or escalation will be carried forward to subsequent time points. For intermittent missing data before the discontinuing study drug due to any reason, the last nonmissing observation (including observation at Week 24) before the intermittent missing data will be carried forward. Randomized patients at Week 24 without at least 1 postrandomization observation will not be included for evaluation for RW ITT Population, with the exception of patients discontinuing study treatment because of an AE, including death.

### 6.3.4. Multiple Imputation

Analysis of continuous efficacy and health outcome variables for long-term ixekizumab treatment analysis will be assessed using the MI method. In the MI analyses, missing data will be imputed so as to estimate what the observations would have been if the patient had not discontinued. Specifically, MI is the partial imputation of non-monotone missing data using

Markov chain Monte Carlo method with the simple imputation model, followed by a sequential regression. For composite scores, the MI analysis will be done at the component level.

## 6.4. Multicenter Studies

This study will be conducted by multiple investigators at multiple sites internationally. The countries will be categorized into geographic regions, Europe and non-Europe, as described in Section 6.2, for analysis.

Descriptive statistics will be provided by subgroups of geographic region: Europe or Non-Europe, and United States (US) or Non-US, for ASAS40 and BASDAI change from baseline at Week 64 for the Long-Term Ixekizumab Efficacy Population.

[figure not shown]
## 6.5. Multiple Comparisons/Multiplicity

The following is a list of primary and major secondary objectives to be tested during Period 2:

1. Primary – proportion of patients who do not experience a flare (Total IXE versus Placebo)
2. Secondary 1 – proportion of patients who do not experience a flare (IXE80Q4W versus Placebo)
3. Secondary 2 – time to the first flare (Total IXE versus Placebo)
4. Secondary 3 – time to the first flare (IXE80Q4W versus Placebo)

A multiple testing strategy using graphical multiple testing procedure (Bretz et al. 2011) for the primary and major secondary objectives will be implemented to control the family-wise type I error rate at a 2-sided  $\alpha$  level of 0.05.

The primary and major secondary endpoints will be sequentially tested in the order, as presented in Figure RHBY.6.1 using the primary statistical method described in Section 6.1.3.1 to compare ixekizumab with placebo. This is a predetermined fixed testing order; thus it is a gatekeeper method. If a test in this sequence is not significant, all the subsequent tests will be considered non-significant (Hsu and Berger 1999). The graphical approach is a closed testing procedure; hence, it strongly controls the family-wise error rate (Hsu and Berger 1999; Alos et al. 2014).

Abbreviations: IXE = ixekizumab; Combined IXE = IXEQ2W + IXWQ4W; Q2W = every 2 weeks; Q4W = every 4 weeks.

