
 To evaluate in patients having achieved a state of sustained remission whether the ixekizumab 80 mg every 2 weeks (Q2W) treatment group or ixekizumab 80 mg every 4 weeks (Q4W) treatment group is superior to placebo in maintaining response after randomized withdrawal 	
 The proportion of patients in the randomized withdrawal population who do not experience a flare during Period 2

 To evaluate in patients having achieved a state of sustained remission whether the combined ixekizumab treatment group is superior to the placebo group in maintaining response after randomized withdrawal 	
 Time to flare for patients in the randomized withdrawal population during Period 2

 To evaluate in patients having achieved a state of sustained remission whether the ixekizumab 80 mg Q2W treatment group or ixekizumab 80 mg Q4W treatment group is superior to placebo in maintaining response after randomized withdrawal 	
 Time to flare for patients in the randomized withdrawal population during Period 2

Objectives	Endpoints

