10.3.1.6. Adjustment for Multiple Comparisons

The primary outcome of proportion of patients who do not experience a flare will be tested for ixekizumab versus placebo at a 2-sided $\alpha=0.05$. The comparison of major secondary objectives (Section 4) will be tested using an appropriate multiple testing approach providing strong control of the familywise error rate (for the primary and major secondary tests) at a 2-sided $\alpha=0.05$. Details of the specific testing methodology (including testing order, interrelationships, type I error allocation, and the associated propagation) will be specified in the SAP.

There will be no adjustment for multiple comparisons for any other analyses.

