## 4. Study Objectives

Objectives	Endpoints
Primary	

 
To evaluate in patients having achieved a state of sustained remission, whether the combined ixekizumab treatment group is superior to the placebo group in maintaining response during Period 2
 
	
 
The proportion of patients in the randomized withdrawal population who do not experience a flare during Period 2
 

Major Secondary	

 
To evaluate in patients having achieved a state of sustained remission whether the ixekizumab 80 mg every 4 weeks (Q4W) treatment group is superior to placebo in maintaining response after randomized withdrawal
 
	
 
The proportion of patients in the randomized withdrawal population who do not experience a flare during Period 2
 

 
To evaluate in patients having achieved a state of sustained remission whether the combined ixekizumab treatment group is superior to the placebo group in maintaining response after randomized withdrawal
 
	
 
Time to flare for patients in the randomized withdrawal population during Period 2
 

 
To evaluate in patients having achieved a state of sustained remission whether the ixekizumab 80 mg Q4W treatment group is superior to placebo in maintaining response after randomized withdrawal
 
	
 
Time to flare for patients in the randomized withdrawal population during Period 2
 

Other Secondary	

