
 
To evaluate in patients having achieved a state of sustained remission whether the combined ixekizumab treatment group, ixekizumab 80 mg Q4W or ixekizumab 80 mg Q2W is superior to the placebo group in maintaining response during Period 2
 
	
 
The proportion of patients in the randomized withdrawal population with a 20% improvement in the Assessment of Spondyloarthritis International Society criteria (ASAS20), a 40% improvement (ASAS40), and improvement of at least 20% and improvement of at least 1 unit in at least 5 of 6 domains in the ASAS (ASAS5/6), ASAS partial remission, clinically important improvement (change of Ankylosing Spondylitis Disease Activity Score [ASDAS] <math>\geq 1.1</math> units), major improvement (change of ASDAS <math>\geq 2.0</math> units), inactive disease (ASDAS <math>< 1.3</math>), and ASDAS <math>< 2.1</math> during Period 2
 
Change from baseline in the individual components of the ASAS response criteria
 
Change from baseline in Bath Ankylosing Spondylitis Disease Activity Index (BASDAI)
 
Proportion of patients with Bath Ankylosing Spondylitis Disease Activity Index 50 (BASDAI50) response from baseline
 
Change from baseline in ASDAS
 
Change from baseline in high sensitivity C-reactive protein (CRP)
 
Change from baseline in Bath Ankylosing Spondylitis Functional Index (BASFI)
 
Change from baseline in the measures of axial mobility: 
 
Bath Ankylosing Spondylitis Metrology Index (BASMI) (linear), and BASMI individual components
 
Chest expansion
 
Change from baseline in occiput to wall distance
 
 
 
Change from baseline in Maastricht Ankylosing Spondylitis Enthesitis Score (MASES) and Spondyloarthritis Research Consortium of Canada Score (SPARCC) enthesitis score
 

Other Secondary	

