**Figure RHBY.6.1. Illustration of graphical multiple testing procedure with initial  $\alpha$  allocation and weights.**

There will be no adjustment for multiple comparisons for any other analyses.

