### **6.10.2. Major Secondary Efficacy Analysis**

The major secondary outcomes are:

- To evaluate in patients having achieved a state of sustained remission whether ixekizumab 80 mg every 4 weeks (Q4W) treatment group is superior to placebo in maintaining response as measured by the proportion of patients in the randomized-withdrawal population who do not experience a flare during the randomized withdrawal-retreatment period
- To evaluate in patients having achieved a state of sustained remission whether the Combined Ixekizumab treatment group is superior to the placebo group in maintaining response after treatment withdrawal as measured by the time to the first flare during the randomized withdrawal-retreatment period
- To evaluate in patients having achieved a state of sustained remission whether the ixekizumab 80 mg Q4W treatment group is superior to placebo in maintaining response after treatment withdrawal as measured by the time to the first flare during the randomized withdrawal-retreatment period.

The primary analysis for categorical major secondary outcomes is a logistic regression analysis with treatment, geographic region, and originating study will be included in the model (Section 6.1.3.1). In the case when logistic regression model does not produce statistical results due to sparse data, Fisher's exact test will be used. Missing data will be imputed using the NRI method (Section 6.3.2).

Kaplan-Meier product limit method will be used to estimate the survival curves for time to the first flare for patients in RW ITT Population during Period 2. The number of patients at risk and experiencing flare by each scheduled visit during Period 2 will be presented by treatment group. The Kaplan-Meier estimate of the proportion of patients experiencing flare will be presented for each visit. Treatment group comparisons will be performed using the log-rank test with strata of geographic region and originating study. A Kaplan-Meier plot of time to the first flare by treatment group will also be provided. See Section 6.1.3 for censored data.

The variable derivations for the major secondary outcomes are described in [Table RHBY.6.4](#).

The treatment group comparisons for the primary and major secondary outcomes will be tested based on the graphical multiple testing procedure detailed in Section 6.5.

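### The SAP's error-controlled family leaves out the two Q2W-versus-placebo flare comparisons that the protocol makes major secondary

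*SAP*

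**What the plan says.** **Protocol.** Section 4, Table RHBY.1 has a major secondary objective to evaluate "whether the ixekizumab 80 mg every 2 weeks (Q2W) treatment group or ixekizumab 80 mg every 4 weeks (Q4W) treatment group is superior to placebo"; its endpoint is the share of patients who stay flare-free during Period 2. A parallel objective covers time to flare. Section 10.3.1.2.1 requires each dose to be compared with placebo. Section 10.3.1.6 states: "The comparison of major secondary objectives (Section 4) will be tested using an appropriate multiple testing approach providing strong control". The level is a two-sided 0.05. It then says what is left to the SAP: "Details of the specific testing methodology (including testing order, interrelationships, type I error allocation, and the associated propagation) will be specified in the SAP".

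**SAP, the controlled family.** Section 4 lists as major secondary "whether the ixekizumab 80 mg every 4 weeks (Q4W) treatment group is superior to placebo in maintaining response after randomized withdrawal" and drops Q2W. Section 6.5 orders four tests: Total IXE on flare-free proportion (primary); Q4W on the same endpoint, worded "proportion of patients who do not experience a flare (IXE80Q4W versus Placebo"; Total IXE on time to first flare; Q4W on time to first flare. Section 6.10.2 agrees, asking "whether ixekizumab 80 mg every 4 weeks (Q4W) treatment group is superior to placebo in maintaining response as measured by the proportion of patients" without flare. Outside this family, "There will be no adjustment for multiple comparisons for any other analyses". Section 6.10.3 repeats this for additional analyses of flare occurrence.

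**SAP, where Q2W remains.** Section 6.1.3.1 requires each regimen to be compared with placebo in all Period 2 analyses. The Other Secondary objective in Section 4 covers "whether the combined ixekizumab treatment group, ixekizumab 80 mg Q4W or ixekizumab 80 mg Q2W is superior to the placebo group in maintaining response", but neither flare endpoint is listed under it. In Table RHBY.6.5, Q2W versus placebo appears in the not-flare row, labelled for the primary and major secondary objectives, and in the time-to-first-flare row, labelled for major secondary objectives.

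**The concern.** The protocol delegates how the major secondary objectives are tested: order, alpha and its propagation. It does not delegate which objectives belong to the family. The SAP nevertheless narrows the family, and its visible text records neither the change nor a reason.

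Two comparisons that the protocol promised to control will therefore be tested at an unadjusted 0.05, with no visible tier in the SAP's objectives and a table label suggesting a higher one. The Week 64 lock (SAP 6.16) is both the unblinding and the analysis of all primary and major secondary objectives. If the status of Q2W is still open then, it can be settled after the p-values are known.

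**Working it through.** **1. The family, side by side**

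| Comparison with placebo | Protocol Section 4 | SAP 6.5 |
|---|---|---|
| Flare-free proportion, combined | Primary | Test 1 |
| Flare-free proportion, Q4W | Major secondary | Test 2 |
| Time to flare, combined | Major secondary | Test 3 |
| Time to flare, Q4W | Major secondary | Test 4 |
| Flare-free proportion, Q2W | Major secondary | Absent |
| Time to flare, Q2W | Major secondary | Absent |

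**2. The plan's power figure, and whether power explains the omission.** Inputs (Protocol 10.1, SAP 5.2): 200 patients, about 100 per regimen, 2:1 to ixekizumab or placebo, flare rates 10% and 70%, two-sided Fisher's exact test at 0.05. This gives about 67 Q2W, 67 Q4W and 66–67 placebo.
- Primary, 133 v 67: exact power over 99.99%, consistent with the stated figure of over 99%.
- Protocol fallback of 150 patients, 100 v 50: over 99.99%, consistent with over 95%.
- Q2W v all placebo, 67 v 67: over 99.99%. Q2W v its own stratum's placebo, 67 v 33: over 99.99%.
- Q2W at 150 patients: 50 v 50, over 99.99%; 50 v 25, 99.97%.

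At the planning rates, lack of power is no reason to leave Q2W out.

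**3. Error over the protocol's flare family when all arms are equal.** In a fixed sequence, nothing can be rejected unless test 1 is. With Q2W tested alongside, the error is P(test 1 or either Q2W test rejects). Its assumption-free bound is 3 × 0.05 = 0.15; if the three were independent it would be 1 − 0.95³ = 0.143. The tests share data, so the value was simulated: 67/67/66 with pooled placebo, 10 four-weekly visits, constant hazard, Wald log-odds-ratio test for the proportion, log-rank for time, two-sided 0.05, no covariates, strata or dropout; 400,000 trials per setting. The common flare rates are assumptions.

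| Common flare rate | Q2W unadjusted beside the sequence | Q2W appended to the sequence |
|---|---|---|
| 40% | 7.8% | 4.8% |
| 50% | 8.4% | 5.0% |
| 60% | 8.3% | 4.8% |
| 70% | 8.5% | 4.8% |

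Counting only rejections that favour ixekizumab, the figures are about 4% and 2.2–2.5%.

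**4. Only Q2W ineffective** (Q4W 10%; Q2W and placebo both 40–70%). The chance of a false claim of Q2W benefit is about 3.0–3.4% unadjusted and 2.5–2.8% gated behind tests 1–4.

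**5. What gating costs.** Chance that both Q2W tests succeed (rates other than 10% and 70% are assumptions; 150 patients means 50 per group):

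| Patients | Ixekizumab v placebo flare rate | Ungated | Gated | Loss (points) |
|---|---|---|---|---|
| 200 | 10% v 70% | >99.9% | >99.9% | about 0 |
| 200 | 20% v 50% | 95.7% | 92.5% | 3 |
| 200 | 20% v 40% | 70.3% | 56.2% | 14 |
| 150 | 20% v 50% | 88.6% | 81.3% | 7 |
| 150 | 20% v 40% | 57.1% | 40.7% | 16 |

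**The case against.** **The SAP is consistent.** Sections 4, 6.5 and 6.10.2 all define the family without Q2W, and 6.5 and 6.10.3 say the remaining flare tests are unadjusted. Presenting a Q2W p-value as major secondary would depart from the SAP, not follow it. This stands, and it makes the error inflation conditional. It does not remove the mismatch with Protocol 10.3.1.6.

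**The table label is over-read.** In Table RHBY.6.5 the label sits with the variable, the comparison list is a standard one, and the not-flare row covers every scheduled visit, so not every test in it can be major secondary. That is fair for the not-flare row. The time-to-first-flare row has no visit-by-visit testing, and neither row marks Q2W as outside the family. The label is a secondary point; the narrowed family is the main one.

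**The protocol says Q2W or Q4W.** One could read this as met by either regimen. Protocol 10.3.1.2.1, however, requires each dose to be compared with placebo, and no visible SAP text adopts the narrower reading.

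**A rationale may be out of sight.** Redacted text follows the SAP objectives, and Figure RHBY.6.1 is not shown. One can therefore say only that no tier is visible, not that none exists.

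**A stronger error claim is tempting.** In the setting where only Q2W is ineffective, two-sided rejections run at 5.7–6.5% unadjusted and 2.6–3.8% gated, from which a reader might infer that gating halves false Q2W claims. Those counts include rejections favouring placebo, which are not claims of benefit. In the benefit direction the reduction is small (step 4).

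**Conclusion.** The point holds as a mismatch between protocol and SAP: two flare comparisons that the protocol makes major secondary, and promises to control, are outside the SAP's controlled family and have no visible tier. It should be corrected, but the primary analysis is not affected.

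A reader might infer that the SAP's testing procedure is faulty or that the trial's error rate is inflated as planned. The documents do not support either: the fixed sequence controls its own four tests at 0.05. The rise to about 7.8–8.5% (about 5% with Q2W appended) arises only if unadjusted Q2W results are presented as major secondary. It also rests on assumed null flare rates, assumed group sizes and simplified unstratified tests. If Q2W results are presented as nominal, there is no inflation, but the trial then makes no controlled Q2W claim although its protocol lists one.

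The handling of mSASSS is a separate mismatch and lends no support to this point. The protocol makes the historical-control comparison major secondary (Table RHBY.1, Section 10.3.3.2); the SAP treats mSASSS as other secondary and descriptive (Section 4, Table RHBY.6.1, Section 6.1.4).

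**What to change.** **Recommended.** In SAP 6.5, after Secondary 3, add Secondary 4 (flare-free proportion, IXE80Q2W versus placebo) and then Secondary 5 (time to first flare, IXE80Q2W versus placebo). Test each at 0.05 only if every earlier test has succeeded. Align SAP Sections 4, 6.10.2 and 6.10.3 and Figure RHBY.6.1, and do so before the Week 64 lock.

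This is a change of wording, one objectives table and one figure. It needs no new data, takes no alpha or power from tests 1–4 and leaves the protocol's flare objectives as they are. The price is that a Q2W claim depends on all four earlier tests; step 5 of the working gives the loss.

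**Alternative, if Q4W is meant to be the only individually controlled regimen.** Mark the Q2W comparisons in the flare rows of Table RHBY.6.5 as other secondary with nominal p-values, and give them that tier in SAP Section 4. Record the departure from the protocol's major secondary list: under Protocol 10.3.1 that means an amendment if a principal feature changes, and otherwise a justification in the clinical study report.

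Reconcile the mSASSS objective between the two documents as a separate item under the same rule.

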**Figure RHBY.6.1. Illustration of graphical multiple testing procedure with initial  $\alpha$  allocation and weights.**

There will be no adjustment for multiple comparisons for any other analyses.

## 6.6. Patient Disposition

The following patient disposition summaries will be provided:

- Patient flow will be summarized for all patients entered into Study RHBY Lead-in Period at Week 0 (Visit 1), being randomized (Group B), or not randomized at Week 24 (Group A), completing at Week 64, Week 104, and Follow-Up Visits 801, 802, and 803, by treatment group as assigned at the beginning of each period.
- Patient allocations by region, country, and center/site will be summarized (numbers and percentages) for patients who entered into the study, randomized at Week 24, discontinued from study treatment, and discontinued from study.

- The number and percentage of patients completing each period by treatment group and primary reason for study treatment discontinuation in:
  - Period 1 (Lead-In Period Safety Population)
  - Period 2 (RW ITT Population, Lead-In Period Safety Population – Group A, and Flare Population with Retreatment)
  - Period 3 (RW ITT Population, Lead-In Period Safety Population – Group A, and Flare Population with Retreatment)
  - Period 4 (Follow-Up Period Population).

Fisher's exact test will be used to test for treatment group differences on patient disposition for the RW ITT Population in Period 2.

Corresponding by-patient listings will also be provided for the variables summarized above.

## 6.7. Patient Characteristics

Patient characteristics will be listed for all entered patients and summarized by treatment assignment group for the following populations at the specified time point:

- All Entered Patients, at Week 0 in RHBY
- Long-Term Ixekizumab Treatment Efficacy Population at Week 0 from originating study
- RW ITT Population, at Week 24 in RHBY
- Ixekizumab Structure Population, at Week 0 in originating studies: for some selected characteristics
- Flare Population with Retreatment, at Week 24 in RHBY
- RW ITT Population by patients with flare and without flare, at Week 24 in RHBY

The continuous variables will be summarized using descriptive statistics (number of patients, mean, standard deviation [SD], minimum, median, and maximum); categorical variables will be summarized using frequency counts and percentages.

Treatment group comparisons for the RW ITT Population will be conducted using Fisher's exact test for categorical data and an analysis of variance (ANOVA) with treatment as a factor for continuous data.

### 6.7.1. Demographics and Important Characteristics

#### Demographics and important characteristics:

- Age (in years): calculated using an imputed date of birth of July 1st in the year of birth collected in the electronic case report form (eCRF). Age will be calculated as:

$$Age = \text{floor}((\text{intck}('month', brthdtc, rfstdtc) - (\text{day}(rfstdtc) < \text{day}(brthdtc))) / 12)$$

where brthdtc = Imputed date of birth, and rfstdtc = subject reference start date (ie, the date when patient is first exposed to study treatment in originating study for Long-Term Ixekizumab Efficacy Population and in study RHBY for All Entered Patients in RHBY, respectively). If rfstdtc is missing, the corresponding informed consent date at the first visit in the originating study will be used.

- Age category: <40 years,  $\geq$ 40 years
- Age category: <50 years,  $\geq$ 50 years
- Age category: <65 years,  $\geq$ 65 years
- Sex
- Race
- Ethnicity
- Geographic region: Europe or Non-Europe
- Country
- Weight (kg)
- Weight category: <70 kg, 70-90 kg, or  $\geq$ 90 kg
- Body mass index (BMI) ( $\text{kg}/\text{m}^2$ ) will be calculated as:

$$BMI (\text{kg} / \text{m}^2) = \frac{Weight (\text{kg})}{(Height (\text{m}) \text{ at Week 0 in originating studies})^2}$$

- BMI category:
  - underweight ( $<18.5 \text{ kg}/\text{m}^2$ )
  - normal ( $\geq 18.5$  and  $<25 \text{ kg}/\text{m}^2$ )
  - overweight ( $\geq 25$  and  $<30 \text{ kg}/\text{m}^2$ )
  - obese ( $\geq 30$  and  $<40 \text{ kg}/\text{m}^2$ )
  - or extremely obese ( $\geq 40 \text{ kg}/\text{m}^2$ )
- Age of onset of axSpA (in years)
- Duration of symptoms since onset (in years) will be calculated using the date of onset of spondylitis disease (as recorded on the *Prespecified Medical History: Axial Spondyloarthritis* eCRF page) as follows:

$$\begin{aligned} & \text{Duration of symptom since onset (years)} \\ &= \frac{\text{Date of informed consent} - \text{Date of onset of axial spondylitis}}{365.25} \end{aligned}$$

- Duration of symptom since onset category: <10 years,  $\geq$ 10 years
- Duration of symptom since onset category: <5 years,  $\geq$ 5 years
- Duration of symptom since onset category: <3 years,  $\geq$ 3 years
- Duration of disease since diagnosis (in years) will be calculated using the date of diagnosis of spondylitis disease (as recorded on the *Prespecified Medical History: Axial Spondyloarthritis* eCRF page) as follows:

$$\text{Duration of disease since diagnosis (years)} \\ = \frac{\text{Date of informed consent} - \text{Date of diagnosis of axial spondylitis}}{365.25}$$

- Human leukocyte antigen B27 (HLA-B27) positivity: n (%)
- Current and/or history of extra-axial involvement overall and separately for: n (%)
  - inflammatory back pain
  - anterior uveitis
  - psoriasis
  - inflammatory bowel disease (including Crohn's disease or ulcerative colitis)
  - dactylitis
  - arthritis
  - enthesitis.
- Originating studies: RHBV, RHBW, or RHBX
- Initial treatment at Week 0 in originating studies: Placebo, Adalimumab, Ixekizumab

